5.6 Premature Termination of the Study

The clinical study may be terminated prematurely or suspended at the request of Health Authorities or if new safety or efficacy information leads to an unfavourable risk benefit judgment for any IP. The Sponsor may discontinue the study if it becomes unjustifiable for medical or ethical reasons, for poor enrolment, or because of discontinuation of clinical development of an IP or withdrawal of an IP or comparator from the market for safety reasons.

Health Authorities and Independent Ethics Committees (IECs) will be informed about the discontinuation of the study in accordance with applicable regulations.

5.7

Definition of End of Study

This study is considered closed when all the e-CRFs are satisfactorily completed and the database is finally locked.

A clinical study protocol may not be considered closed as long as:

- Any patient is still receiving any IP;
- Visits specified by the protocol are still taking place;
- Procedures or interventions according to the protocol are still being undertaken in any patient;
- The post-treatment follow up period, defined in the clinical study protocol as being part of the study, has not yet been completed for any patient.

6

Investigational Product and Other Drugs Used in the Study

The term “Investigational Product” (IP) refers to an active substance or a placebo being tested or used as a reference therapy in a clinical study, including products that have a marketing authorization but are formulated, packaged, or administered differently from the authorized form, used for an unauthorized indication, or used to gain further information about the authorized form.

6.1

Description of the Investigational Product

In this study, the term “Investigational Product” (IP) refers to D-asp or placebo.

Investigational Product

D-asp is commercialized and approved in Italy for its use in humans as a dietary supplement.

Underlying therapy

D-asp 2660mg or placebo will be administered once daily as add-on to conventional therapies (IFN beta-1a 44mcg TIW for patients without relapse and IFN beta-1a 44mcg TIW plus methylprednisolone i.v. for patients with relapse, for 5 consecutive days at 1000mg once daily).

Patients and investigators involved in both clinical and neurophysiological and MRI assessments will be blinded to patients' group allocation.

Draft Labels of IP are inserted in [Appendix VI](#).

6.2

Dosage and Administration

D-asp at the dose of 2660mg or placebo will be administered once a day for 24 weeks in the form of identical oral solution preparations. The IP (D-asp or placebo) should be administered preferably after the meal.

The content of a sachet should be cleared out in an empty glass. Then approximately 100 ml of still water should be added and the product should be mixed until the effervescence is ended. The product should be administered immediately after the preparation.

Placebo will be undistinguishable from D-asp in terms of packaging, size, colour, weight, appearance, taste and mode of administration.

6.3

Assignment to Treatment Groups

Patients presenting with a relapse and meeting the eligibility criteria during a screening period of 3-5 days will be randomised in a 1:1 ratio via e-CRF to:

- D-asp,
- Placebo.

It is planned to randomise 80 patients with relapse. Randomisation will be stratified according to age (<30 years vs. \geq 30 years) and site location (Rome+Naples+Pozzilli vs. the other sites).

Patients without a relapse will be recruited only at the Pozzilli site and will be randomised in a 1:1 ratio via e-CRF to:

- D-asp,
- Placebo.

It is planned to randomise 40 patients without a relapse. Randomisation will be stratified according to age (<30 years vs. \geq 30 years)

The randomisation list will be in a balanced block design and will be centralized. In each site, eligible patients will be sequentially assigned to the next study number as they present themselves for the study, starting from the lowest number provided for each centre. If a patient discontinues from the study, the patient number will not be reused, and the patient will not be allowed to re-enter the study.

It will be the responsibility of the Investigator (or designee) to explain, and make sure patients fully understand any appropriate treatment related information.

6.4

Non-investigational Medicinal Products to be Used

Treatment with the IP (D-asp 2660mg once daily or placebo) will be administered as add-on to conventional therapies (IFN beta-1a 44mcg TIW for patients without relapse and IFN beta-1a 44mcg TIW plus methylprednisolone i.v. for patients with relapse, for 5 consecutive days at 1000mg once daily).

The prescription of IFN beta-1a in the individual patients will be totally independent from his/her inclusion in the study.

IFN beta-1a will be prescribed exclusively following the indications approved by the Italian Regulatory Authorities, and following the clinical routine of each participating site.

IFN beta-1a will not supplied by the Sponsor and the Investigator should use commercially available sources.

6.5

Concomitant Medications and Therapies

All concomitant medications taken by the patient during the study, from the date of signature of informed consent are to be recorded in the appropriate section of the e-CRF, noting the name, dose, duration and indication of each drug. Nondrug interventions and any changes to a concomitant medication or other intervention should also be recorded in the e-CRF.

6.5.1 Permitted Medicines

The investigator and/or study personnel will record all concomitant medications taken by the patient during the study from the date of signature of informed consent.

Any medications other than those excluded by the protocol, which are considered necessary for the patient's welfare, and which do not interfere with the study medication, may be given at the discretion of the investigator. Administration of all concomitant medications must be reported in the appropriate section of the e-CRF along with dosage information, dates of administration and reasons for use. If the study drug is discontinued, all continuing medication taken must be recorded in the e-CRF until the end of the study. The following conditions should be addressed by the investigator with particular attention, documenting specifically the reasons for the administration of a concomitant medication for the following cases:

- For a MS related condition (e.g. pain, fatigue or weakness, bladder dysfunction, spasticity, etc.);
- For a medical condition already reported in the patients Medical History (e.g. any form of pain, especially lumbar pain and headache, depression, etc.) and/or in the Family History (primary headache, insomnia etc.);
- For prophylactic use (e.g. flu-like symptoms, neuroprotection, etc.).

6.5.2 Prohibited Medicines

The following medicines are prohibited for the total study duration, i.e. from the screening visit to the end of treatment or ET visit:

- Any concomitant treatment for MS, i.e. other IFN therapy to IFN beta 1a 44mcg TIW, glatiramer acetate, dimethyl fumarate, fingolimod, teriflunomide, natalizumab, alemtuzumab, mitoxantrone;
- Concomitant treatment with drugs that may alter synaptic plasticity (e.g. cannabinoids);
- Any corticosteroids therapy (apart from the supportive therapy with methylprednisolone i.v. for patients with relapse for 5 consecutive days at 1000mg once daily);
- Any other immunosuppressive agents other to methylprednisolone i.v. for patients with relapse for 5 consecutive days at 1000mg once daily, given as monotherapy or combination therapy.

If a prohibited concomitant drug is administered during the study, the patient should be discontinued from the study.

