The study plan will include five visits in total. An Early Termination (ET) visit will be performed in case of treatment discontinuation.

The patients will be assessed at Screening (Visit -1, Day -5/-3), Baseline (Visit 0, Day 0-Week 0), and at Week 8 (Visit 1), Week 12 (Visit 2) and Week 24 (Visit 3). A \pm 3-day window is allowed for the planned days of the visits.

Clinical assessments and cognitive impairment (EDSS, 25-foot Timed Walk [25WFT]; 9 Hole PEG Test [9HPT]; SDT; Low Contrast Letter Acuity test; MFIS and FSS) will be performed in all patients at screening (Visit -1, Day -5/-3), baseline (Visit 0, Day 0-Week 0), and at Week 8 (Visit 1), Week 12 (Visit 2) and Week 24 (Visit 3) from the first day of treatment with D-asp/placebo, as well as at the ET visit in case of treatment discontinuation. In the case of occurrence of a relapse, clinical assessments will be recorded during the inpatient ward access by neurologist's experts in the diagnosis and treatment of MS.

Neurophysiological assessments (LTP and recruitment curve) will be performed at the centre of the PPD only in patients without relapse, at baseline (Visit 0, Day 0-Week 0), and at Week 8 (Visit 1), Week 12 (Visit 2) and Week 24 (Visit 3) from the first day of treatment with D-asp/placebo, as well as at the ET visit in case of treatment discontinuation.

Immune-phenotype and immunometabolic analysis will be performed in patients enrolled in the centres of Rome, Naples and Pozzilli in samples obtained at baseline (Visit 0, Day 0-Week 0) before receiving corticosteroids, and after 8 (Visit 1) and 12 (Visit 2) weeks from the first day of treatment with D-asp/placebo, as well as at the ET visit in case of treatment discontinuation.

Brain MRI will be performed according to local clinical practice at screening (Visit -1, Day -5/-3), baseline (Visit 0, Day 0-Week 0) or previous MRI will be evaluated if available and 24 (Visit 3) weeks from the first day of treatment with D-asp/placebo, as well as at the ET visit in case of treatment discontinuation, whenever it will be available.

Adherence to treatment will be assessed after 8 (Visit 1), 12 (Visit 2) and 24 (Visit 3) weeks from the first day of treatment with D-asp/placebo, as well as at the ET visit in case of treatment discontinuation.

The occurrence of adverse events (AEs) will be monitored over the total study duration.

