5.5 Criteria for Subject Withdrawal

5.5.1 Withdrawal from Study Therapy

A patient must be withdrawn from IP if any of the following occur:

- Patient withdraws consent;
- Patient is lost to follow up;
- Participation in another clinical study;
- Occurrence of an exclusion criterion which is clinically relevant and affects the patient's safety, if discontinuation is considered necessary by the Investigator and/or Sponsor;
- Therapeutic failure requiring urgent additional drug;
- Any events that unacceptably endanger the safety of the patient;
- Occurrence of adverse events, if discontinuation of study drug is desired or considered necessary by the Investigator and/or the patient;
- Occurrence of pregnancy;

- Serious intercurrent illness or significant worsening of intercurrent illness;
- MS-related neurological events requiring steroid treatment (in this case, an ET visit will be conducted, during which a blood sample will be taken before the start of the steroid treatment);
- Patients without relapse at entry in the study that will relapse during the 24-week treatment phase.

If a patient prematurely withdraws from the IP at any time during the study, he/she will undergo all assessments requested at the ET visit ([Section 7.1](#)) as soon as possible after his/her last injection. In any case, the appropriate electronic Case Report Form (e-CRF) section including the reason(s) for withdrawal from the IP must be completed.

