5.5.2 Withdrawal from the Study

Patients may withdraw from the study at any time without giving a reason.

Patient must be withdrawn from the study if a patient withdraws the informed consent. Withdrawal of consent will be considered as a withdrawal from the study.

Patient must be also withdrawn from the study if he/she participates in another clinical study.

If a patient has failed to attend scheduled study assessments, the Investigator must determine the reasons and the circumstances as completely and accurately as possible.

If a patient fails to return for assessments, attempts should be made to contact the patient to determine whether or not the reason for not returning is an adverse event. Likewise if a patient declares his/her wish to discontinue the study, e.g., for personal reasons, an attempt should be made to establish whether or not the true reason is an adverse event (bearing in mind the patient is not obliged to state his/her reasons).

If a patient prematurely withdraws from the study at any time, he/she will undergo all assessments requested at the ET visit ([Section 7.1](#)) as soon as possible after his/her last injection. In any case, the appropriate e-CRF section including the reason(s) for withdrawal from the study must be completed.

The patient who has withdrawn early will receive other appropriate treatment, in accordance with the study site's standard of care and generally accepted medical practice and depending on the patient's individual medical needs.

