8.3 Analysis Sets

Intention-to-treat (Full Analysis Set)

The intention-to-treat (ITT) population will include all patients enrolled into the study and assigned to the randomised treatment.

Per-protocol

The per-protocol (PP) population will include all patients who have been treated according to protocol and fulfil the following criteria:

- Compliance with all entry criteria;
- Absence of major protocol violations;
- Adequate compliance with study medication.

Safety

The safety population will include all patients who have received at least one dose of planned study treatment.

The number and percentage of the patients included in the analysis populations will be reported in a table showing the reason of exclusion for all patients enrolled into study.

The efficacy analysis will be performed in the ITT population. In order to assess the robustness of the results, the analysis of the primary endpoint will be repeated in the PP population.

The safety analysis will be performed in the safety population.

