8.4 Description of Statistical Analyses

8.4.1 General Considerations

Methods described here represent the outline of the intended methods.

A Statistical Analysis Plan (SAP) will be produced before the database lock and will contain full details of all planned summaries, listings and analyses.

All summaries and listings will be performed using Statistical Analysis Software (SAS) System software (version 9.2 or later). Unless otherwise specified, all statistical hypotheses will be tested at the 5% significance level ($\alpha = 0.05$) against two-sided alternatives, and corresponding 95% confidence intervals (CI) will be reported as appropriate.

For endpoints measured over time, descriptive statistics (for continuous variables) or frequency count (for categorical data) will be summarized by each time point.

Demographic and clinical characteristics at baseline will be summarized as frequency distributions (for categorical variables) and descriptive statistics of mean, standard deviation, median, minimum and maximum (for continuous variables).

All collected variables will be tested for normality and homogeneity of variance by using Kolmogorov Smirnov and Levene tests.

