8.4.2 Analysis of Primary Endpoint

The comparison between the proportions of recoveries at 8 weeks in patients treated with D-aspartate and patients treated with placebo will be based on descriptive statistics (difference, relative risk and/or odds ratio) and on the chi-square test.

A set of exploratory analyses is planned. First, a multiple logistic regression model will be fitted to the data with recovery at 8 weeks as the dependent variable and age, sex, current DMT use, disease course, severity of relapse, and random assignment as covariates, to adjust for imbalances between the treatment groups.

Second, the time to recovery will be computed for each patient and included as the dependent variable in a multivariate Cox model, with all the above mentioned variables as covariates. Patients not recovered will be censored at last observation.

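### Sections 6.5.2, 5.5.1 and 5.5.2 disagree on whether a relapse patient given a prohibited drug stays in follow-up; an exit before Week 8 leaves only an off-schedule early termination score with no stated role in the primary analysis

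*Combined protocol and SAP*

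**What the plan says.** **Leaving treatment or the study**

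- Section 6.5.2 bars other MS therapies, drugs that alter synaptic plasticity, corticosteroids beyond the 5-day methylprednisolone course, and other immunosuppressants, from screening to end of treatment or the ET visit. It then says: "If a prohibited concomitant drug is administered during the study, the patient should be discontinued from the study".
- Section 5.5.1, headed as withdrawal from study therapy, lists "MS-related neurological events requiring steroid treatment (in this case, an ET visit will be conducted" and "Therapeutic failure requiring urgent additional drug".
- Section 5.5.2 says "Patient must be withdrawn from the study if a patient withdraws the informed consent" and adds entry into another clinical study. It does not mention a prohibited drug.

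**Follow-up**

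- Section 5.1 says that clinical assessments, including the EDSS, "will be performed in all patients at screening", baseline and Weeks 8, 12 and 24. It ties the ET visit to stopping treatment.
- Section 7.1 ties the ET visit to leaving the study. The visit repeats the Visit 3 procedures, which include the EDSS.
- Section 6.5.1 expects medication to be recorded to the end of the study after study drug stops.

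**Analysis**

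- Section 8.3: "The intention-to-treat (ITT) population will include all patients enrolled into the study and assigned to the randomised treatment".
- Section 8.4.2: the comparison of recovery at 8 weeks "will be based on descriptive statistics (difference, relative risk and/or odds ratio) and on the chi-square test". It gives no rule for a missing outcome. Its only rule for incomplete follow-up is censoring in the exploratory Cox model.
- Section 8.1 words the endpoint as a return to baseline inside an 8-week span. Sections 8.2.1 and 8.4.2 word it as recovery at the 8-week point.
- Section 8.4.1: "A Statistical Analysis Plan (SAP) will be produced before the database lock and will contain full details". No separate SAP is in the supplied text.

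**The concern.** The primary endpoint rests on 80 patients who have just relapsed on interferon. Those who need more steroids, or another MS drug, before Week 8 are likely, though not certain, to be the ones not recovering. If they leave the study at that moment, Week 8 information is lost selectively. Leaving them out would overstate recovery rates and shift the comparison toward the arm that loses more of them.

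The ET score does not settle this. It is taken as soon as possible after exit, not at Week 8. For steroid-requiring events, 5.5.1 places the blood sample at that visit before steroids start, so the FS score is probably taken during the acute event. Whether it counts depends on which wording of the endpoint applies.

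Because the sections disagree, two sites could also treat the same patient differently, one keeping the Week 8 visit and one not. A later SAP can add a counting rule, but it cannot recover an assessment that was never made.

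**Working it through.** **Step 1: which exits matter.** The ban in 6.5.2 runs to Week 24. An exit before Week 8 removes the scheduled primary score. A later exit affects only the Week 12 and/or Week 24 endpoints.

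**Step 2: the sections side by side, for a relapse patient given further steroids at, say, Week 4.**

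| Section | Status after the event | Week 8 FS score |
|---|---|---|
| 6.5.2 | Out of the study | Not taken; ET score only |
| 5.5.1 | Off IP, sent to an ET visit | Not expressly kept or dropped |
| 5.5.2 | A prohibited drug is not a listed reason to leave | Not addressed |
| 5.1 | ET follows stopping treatment; assessments are for all patients | Can be read as kept |
| 7.1 | ET follows leaving the study | No visit after exit is described |

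**Step 3: the plan's own sample size (8.1).** Inputs: 40% versus 70%, one-sided 0.05, 80% power, 40 per arm. The mean rate is 0.55.

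n = [1.645·√(2·0.55·0.45) + 0.842·√(0.4·0.6 + 0.7·0.3)]² / 0.30² = (1.157 + 0.565)² / 0.09 = 32.9, so 33 per arm.

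With continuity correction, (n/4)·[1 + √(1 + 4/(0.30n))]² = 39.3, so 40 per arm. The stated figure therefore matches the corrected formula. Section 8.4.2 does not say which version of the chi-square test will be used, so both are shown.

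**Step 4: effect of exits.** The exit rates are assumptions. Each of 40 patients per arm is observed recovered, observed non-recovered or exited before Week 8. Exited patients are left out. The test is the pooled z, uncorrected or with correction 0.5(1/n₁ + 1/n₂), by exact enumeration. True recovery is 40% in both arms, and all exits are non-recovered unless stated.

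| Exits, placebo/D-asp | One-sided error, uncorrected | Corrected |
|---|---|---|
| None | 4.7% | 2.8% |
| 10%/10% | 5.1% | 3.0% |
| 5%/10% | 7.6% | 4.7% |
| 5%/15% | 11.2% | 7.3% |
| 15%/5% | 2.0% | 1.1% |
| 5%/15%, 80% of exits non-recovered | 7.8% | 4.8% |
| 5%/15%, exits unrelated to recovery (60% non-recovered) | 5.1% | 3.0% |

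The mechanism at 5%/15%: the expected observed rates are 0.40/0.95 = 42.1% on placebo and 0.40/0.85 = 47.1% on D-asp, a difference of 5.0 points with no true effect. Two-sided, the default in 8.4.1, a 5%/15% split in either direction gives 7.3% / 4.3%.

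Power for 40% versus 70% with exits of 15%/5% falls from 85.7% to 76.0% uncorrected, or from 79.8% to 67.6% corrected. The observed rates become 0.40/0.85 = 47.1% and 0.70/0.95 = 73.7%, so the 30-point difference shrinks to 26.6.

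**Step 5: the counting rule can decide a close result.** Take 4 missing per arm and recoveries of 14/36 on placebo and 21/36 on D-asp. The uncorrected one-sided p is 0.049 with missing patients left out (z = 0.1944/0.1178 = 1.65) and 0.057 with them counted as not recovered (14/40 versus 21/40, z = 0.175/0.1109 = 1.58).

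**Step 6: counting missing as not recovered is not free of bias.** If 60% of missing patients are truly non-recovered and true recovery is 40% in both arms, one-sided error at 15%/5% missing is 10.1% / 6.3%. With only 2 versus 1 of 40 missing (5%/2.5%) it is 5.8% / 3.4%, and the other way round 4.0% / 2.3%.

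**The case against.** The strongest reply has four parts.

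1. **The contradiction is modest.** The 5.5.1 list also contains withdrawn consent, loss to follow-up and entry into another study, so being listed there does not mean that the patient stays in the study. The protocol partly merges the two kinds of exit. This stands, and it widens the fix: 5.5.1 exits have no express Week 8 visit either, so rewording 6.5.2 alone would not be enough.
2. **The counting rule is deferred.** Section 8.4.1 leaves full details to a SAP, and 8.1 speaks of a rigid intention-to-treat approach that lowers recovery rates. That fits counting missing patients as not recovered better than dropping them. This stands too: the absent rule is deferred detail, not proof that patients will be dropped. It does not answer the loss of follow-up.
3. **The error scenarios are strained.** If exits follow poor recovery and the drug has no effect, exits should be about equal, and error is then near nominal. The 11.2% needs three times as many exits on D-asp with every exit non-recovered, and the documents give no reason to expect that. Fair: the case is illustrative.
4. **The study is a pilot and calls itself exploratory.** This limits severity, but keeping visits already scheduled is cheap.

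A reader might also infer that 6.5.2 destroys the primary outcome of every patient given a prohibited drug. The documents do not support that. Exits after Week 8 leave the primary score intact, and the ET visit does record an EDSS/FS score.

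**Conclusion.** The concern holds in limited form and should be fixed. The exit and follow-up sections conflict. A relapse patient who leaves before Week 8 is assured only an off-schedule FS score with no stated role in the primary analysis. The loss is likely related to poor recovery, so it can bias the primary comparison if exits differ between arms.

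The size depends on assumed exit rates. Among the cases that leave exits out, the continuity-corrected test, which matches the stated 40 per arm, exceeds 5% one-sided only at 5%/15% with all exits non-recovered. The reverse split makes the test conservative and costs power.

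It would be tempting to conclude that the design favours D-asp. The documents do not support this, because the direction depends on which arm loses more patients and nothing in the plan predicts that. Nor do they show that missing patients will be excluded. Confidence is medium.

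**What to change.** **Main change.** Reconcile 6.5.2, 5.5.1, 5.5.2, 5.1 and both ET descriptions in 7.1. State that all randomised relapse patients keep the scheduled Week 8, 12 and 24 EDSS/FS assessments after IP stops or a prohibited drug is given, unless consent is withdrawn. This concerns data collection only. It leaves unchanged when IP stops and what care is given.

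**Secondary change.** Before unblinding, state in 8.4.2 or the SAP:

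- how a Week 8 outcome that is still missing counts, for example as not recovered with all randomised relapse patients in the denominator, which is consistent with the basis of the control rate in 8.1;
- whether an ET score before Week 8 counts, using one wording of the endpoint throughout;
- one sensitivity analysis with the other handling.

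**Order and cost.** Retained follow-up comes first, because counting missing as not recovered does little harm only when few outcomes are missing. The cost is protocol wording, a few already scheduled visits, and possibly slightly lower observed recovery rates.
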